4.4 Interim Analysis

An interim analysis was conducted in 2016 to support the ABT-493/ABT-530 initial marketing applications (NDA/MAA). There is no multiplicity adjustment for the interim analysis as no hypothesis testing was performed. The final analysis will be conducted when all subjects enrolled in the study have completed the follow-up period.

5.0 Analysis Populations

5.1 Definition for Analysis Populations

All enrolled subjects include subjects who may have received re-treatment prior to enrollment in Study M13-576. The full analysis set is defined as all subjects who received an ABT-493- and/or ABT-530-containing regimen at any dose level in a previous AbbVie Phase 2 or 3 study and enroll in this study without receiving retreatment prior to enrolling in this study. Therefore, subjects who received re-treatment prior to enrollment in this study will be excluded from the full analysis set. In addition, subjects who enrolled without meeting inclusion criterion 2 (e.g., subjects who were treated with SOF + DCV in the prior AbbVie study, Study M13-594) will be excluded from the full analysis set.

A listing of subjects excluded from the full analysis set will be provided.

All demographic, efficacy, and safety analyses described in this SAP will be conducted on the full analysis set, unless otherwise specified.

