### **5.2.1 Inclusion Criteria**

A subject will be eligible for study participation if he or she meets the following criteria:

1. The subject is male or female 18 years of age or older.
2. The subject has received at least one dose of an ABT-493- and/or ABT-530 containing regimen in a prior AbbVie HCV Phase 2 or 3 study (see Appendix D for list of eligible prior studies).
3. The interval between the last dose of the AbbVie DAA therapy from the previous clinical study and enrollment in Study M13-576 must be no longer than 2 years for subjects who have not been retreated. Subjects who have been treated with a commercially-available anti-HCV treatment may be enrolled greater than 2 years after the last dose of the AbbVie DAA therapy from the previous clinical study.
4. The subject must voluntarily sign and date the informed consent form approved by an Independent Review Board or Ethics Committee prior to the initiation of any study-specific procedures.
5. Subject completed the post-treatment period of an eligible prior study.

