### **5.3.2 Efficacy Variables**

The primary efficacy outcome variables are:

1. The percentage of subjects who maintain SVR out of those who achieved SVR12 in the prior study with an ABT-493- and/or ABT-530-containing regimen.
2. The percentage of subjects who relapse or have new HCV infection at any time up to the last follow-up in this study out of subjects who achieved SVR12 in the previous study and enroll in this study.

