## **8.0 Statistical Methods and Determination of Sample Size**

### **8.1 Statistical and Analytical Plans**

Analyses will be conducted on all subjects who enroll in this study without receiving re-treatment prior to enrolling in this study, denoted as the full analysis set. Subjects who are virologic failures who receive re-treatment prior to enrollment in this study will be summarized separately and are excluded from the full analysis set.

Descriptive statistics will be provided for demographic variables for all subjects in the full analysis set.

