6.3 Missing Data Imputation

The values of SVR₄, SVR₁₂, and SVR₂₄ will be derived from the previous study as needed

For subjects in the full analysis set, if a subject starts another treatment for HCV, then all HCV RNA values for this subject measured on or after the start date of the new HCV treatment will be excluded from the analyses of SVR and virologic failure. The subject will be considered a failure for summaries of viral response at all time points after the start of the new HCV treatment.

Missing Data Imputation for Virologic Failure

If HCV RNA values from the central laboratory are missing but a local laboratory value is present in the appropriate time period, then the local laboratory value will be used to assess post-treatment relapse.

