Relapse_{late} = confirmed HCV RNA \geq LLOQ at any time after the SVR₁₂ assessment time point for a subject who achieved SVR₁₂ and has post-SVR₁₂ HCV RNA data available, excluding reinfection (derived from both studies).

Relapse_{overall} = confirmed HCV RNA ≥ LLOQ between end of treatment and up to and including the last HCV RNA measurement collected in Study M13-576 for a subject with HCV RNA < LLOQ at Final Treatment Visit who completed treatment, excluding reinfection.

 $SVR_{overall}$ = HCV RNA < LLOQ between the end of treatment and up to and including the last HCV RNA measurement collected in Study M13-576 without any confirmed quantifiable (\geq LLOQ) post-treatment value before value.

Only subjects who have at least one post-treatment HCV RNA value will be included in analyses of relapse. If the last available post-treatment value is \geq LLOQ, then the subject will be considered a relapse (i.e., will not require confirmation).

[figure not shown]
HCV reinfection is defined as confirmed HCV RNA ≥ LLOQ after the end of treatment in a subject who had HCV RNA < LLOQ at Final Treatment Visit, along with the post treatment detection of a different HCV genotype, subtype, or clade compared with baseline, as determined by phylogenetic analysis of the NS3 or NS5A, and/or NS5B gene sequences. Reinfection in the case of the same HCV subtype is defined as a clade switch, as indicated by the lack of clustering between the baseline and post-treatment sequences by phylogenetic analysis. If phylogenetic analysis is not possible due to technical difficulties, HCV reinfection may be determined with a confirmed HCV genotype or subgenotype switch by the Versant HCV Genotype Inno-LiPA Assay v2.0 or Sanger assay.

Post-treatment relapse is defined as described earlier (**Relapse**₁₂, **Relapse**_{late}, **Relapse**_{overall}), and no genotype, subtype, or clade switch compared with baseline as determined by phylogenetic analysis of the NS3 or NS5A gene sequences. If phylogenetic analysis is not possible due to technical difficulties, the subject will be defined as having a post-treatment relapse unless an HCV genotype or subgenotype switch is confirmed by the Versant HCV Genotype Inno-LiPA Assay v2.0 or Sanger assay.

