10.2 Efficacy Analyses

The following efficacy analyses will be conducted on the full analysis set including data up to the last follow-up in this study prior to any HCV re-treatment. For subjects in the

[figure not shown]

full analysis set, HCV RNA measurements taken after the start of another anti-viral HCV treatment (after completion of AbbVie DAA treatments in previous study) will be excluded from the analyses.

The number and percentage of subjects in the full analysis set who achieved SVR₁₂ in the previous study will be summarized overall and by study. A listing of subjects in the full analysis set who did not achieve SVR₁₂ will be provided.

Based on the full analysis set, the number and percentage of subjects who maintain SVR in this study among those who achieved SVR₁₂ in the previous study will be summarized, overall and by visit. Study visits will be displayed as Post-Treatment Weeks 24, 36, 48, 60, 72, 84, 96, 108, 120, 132, 144, and 156. For each visit, the denominator will indicate the number of subjects in the full analysis set who achieved SVR₁₂ and have HCV RNA data within the corresponding visit window. For the overall summary, the denominator will indicate the number of subjects in the full analysis set who achieved SVR₁₂. Overall maintenance of SVR is defined as no confirmed HCV RNA ≥ LLOQ after the SVR₁₂ timepoint (from the previous study) through the last HCV RNA measurement in this study. Confirmation of quantifiable HCV RNA values can occur among any two consecutive HCV RNA values; either both during the same visit window or at the end of a visit window and in the next window. The visit window corresponding to the first occurrence of the confirmed HCV RNA ≥ LLOQ will be counted as having the failure. If the last available value in the study is \geq LLOQ, then the subject will be considered as not maintaining SVR (i.e., will not require confirmation). The summary will include the subject number and the visit window corresponding to the first occurrence of quantifiable HCV RNA.

Among the subjects in the full analysis set who achieved SVR₁₂ in the previous study, a listing of subjects who do not maintain SVR will be provided with subject number, previous study number, the reason (relapse or reinfection) for not maintaining SVR, days from study drug end date to relapse or reinfection, and whether the relapse or reinfection occurs before or after enrolling into this study.

[figure not shown]

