The number and percentage of subjects who relapse (see **Relapse**_{late} definition) at any time up to the last follow-up in this study will be summarized out of subjects in the full analysis set who achieved SVR₁₂ in the previous study. In addition, the number and percentage of subjects in the full analysis set who relapsed anytime (see **Relapse**_{overall} definition) or have new HCV infection (see definition of reinfection) anytime will be summarized.

The time to relapse (**Relapse**_{overall}) or new HCV infection (i.e., reinfection) from the end of DAA treatment for subjects who achieved HCV RNA < LLOQ at the end of treatment in the previous study will be displayed graphically using Kaplan-Meier curves. Similarly, the time to relapse (**Relapse**_{late}) or new HCV infection (i.e., reinfection) from the SVR₁₂ time point for the subset of subjects who achieved SVR₁₂ in the previous study will also be displayed graphically using Kaplan-Meier curves. These summaries will be separate for subjects who have probable relapse as distinguished from subjects who have probable new HCV infection (i.e., reinfection) based on the definitions of relapse and reinfection in Section 10.1.

For the first Kaplan-Meier curve among subjects with final on-treatment HCV RNA < LLOQ, time to event will be measured as the number of days from the last dose of study drug (in the previous study) to event or censoring time. Subjects who do not relapse or were not reinfected will be censored at the date corresponding to the last available HCV RNA measurement.

For the second Kaplan-Meier curve among subjects who had achieved SVR₁₂, time to event will be measured as the number of days from the nominal day of SVR₁₂ assessment to event or censoring time. Subjects who do not relapse or were not reinfected will be censored at the date corresponding to the last available HCV RNA measurement.

For both subjects in the full analysis set and subjects excluded from the full analysis set, a listing of subjects who are re-treated will be provided specifying whether the re-treatment occurs before or after enrolling into the study, prior AbbVie regimen, HCV re-treatment regimen, and SVR₁₂ outcome.

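### The full analysis set drops SVR12 achievers who lost response and were re-treated before Day 1, so any resulting bias favours durability

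*SAP*

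**What the plan says.** - **Analysis set.** SAP 5.1: "subjects who received re-treatment prior to enrollment in this study will be excluded from the full analysis set". Protocol 8.1 first limits the set to subjects who enrol without earlier re-treatment, then says that virologic failures "who receive re-treatment prior to enrollment in this study will be summarized separately and are excluded from the full analysis set".
- **Use of the set.** SAP 10.2 on maintained SVR: "For the overall summary, the denominator will indicate the number of subjects in the full analysis set who achieved" SVR12. The late-relapse percentage and the listing of subjects who do not maintain SVR use the same set. So does the second Kaplan-Meier curve, where "time to event will be measured as the number of days from the nominal day of" the SVR12 assessment. Protocol 8.1.1 also takes its denominators from the full analysis set.
- **Endpoint definition.** Protocol 5.3.2, second primary variable, and the synopsis count relapse or new infection among subjects who achieved SVR12 "in the previous study and enroll in this study". Neither sets a condition on re-treatment.
- **Who may enter.** Under inclusion criterion 3 (Protocol 5.2.1), subjects given a commercial anti-HCV regimen "may be enrolled greater than 2 years after the last dose of the AbbVie DAA therapy from the previous clinical study". The criterion is not confined to subjects who missed SVR12.
- **Failures before Day 1.** SAP 10.1 defines late relapse as "excluding reinfection (derived from both studies"), and the non-maintenance listing in SAP 10.2 records whether the event came before or after enrolment.
- **Re-treatment within the set.** SAP 6.3: "The subject will be considered a failure for summaries of viral response at all time points after the start of the new HCV treatment".

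**The concern.** An SVR12 achiever would ordinarily be treated for HCV again only because viraemia had returned. For this endpoint, being re-treated before Day 1 is therefore a marker of the outcome, and excluding on it takes out failures and no successes. Whether a failure before enrolment counts then depends on how quickly the subject was treated: one still untreated at Day 1 is counted, one already treated is not.

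The study is descriptive and has no hypothesis test, so the durability percentage is itself the main result. Late failures are likely to be few, so one or two removals can change the failure count appreciably or turn it into zero.

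**Working it through.** **1. How four SVR12 achievers who enrol are handled**

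| Course after SVR12 | In full analysis set? | Overall result |
|---|---|---|
| HCV RNA stays below LLOQ | Yes | Maintained |
| Confirmed viraemia before Day 1, not re-treated by Day 1 | Yes | Not maintained |
| Confirmed viraemia before Day 1, commercial re-treatment before Day 1 | No | Not counted |
| Confirmed viraemia after Day 1, with or without later re-treatment | Yes | Not maintained |

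Only the third row leaves the endpoint, and it holds only failures.

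**2. Inputs.** The documents give no expected durability rate and no sample size calculation, so there is no figure to reproduce. The only count is an anticipated enrolment of about 400, with SVR12 achievers and virologic failures together. The following are assumptions:
- D, SVR12 achievers in the full analysis set: 200 to 400
- r, failures counted among them: 0 to 4
- k, SVR12 achievers excluded because re-treated before Day 1: 0 to 5

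**3. Formulas**
- Full analysis set: (D − r)/D
- With the k subjects restored as failures: (D − r)/(D + k)
- Overstatement: (D − r)/D − (D − r)/(D + k), which is never negative and is zero when k = 0

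**4. Results (maintained SVR)**

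| D | r | Full analysis set | k = 1 | k = 2 | k = 5 |
|---|---|---|---|---|---|
| 400 | 2 | 398/400 = 99.50% | 398/401 = 99.25% | 398/402 = 99.00% | 398/405 = 98.27% |
| 300 | 2 | 298/300 = 99.33% | 298/301 = 99.00% | 298/302 = 98.68% | 298/305 = 97.70% |
| 200 | 0 | 200/200 = 100% | 200/201 = 99.50% | 200/202 = 99.01% | 200/205 = 97.56% |

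One excluded subject moves the figure by about 0.25 points at D = 400 and 0.50 points at D = 200. Five move it by about 1.2 to 2.4 points. On the failure scale, with D = 400 and r = 2, restoring two subjects doubles the rate from 2/400 = 0.50% to 4/402 = 1.00%. The exact 95% limits for maintained SVR go from 98.21–99.94% to 97.47–99.73%. The shift is thus modest against sampling error, but it has only one direction.

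**5. Kaplan-Meier curve from SVR12.** Membership of the set requires no re-treatment up to Day 1, which is unknown at the curve's time zero. SVR12 is at day 84, or 84/30.5 = 2.75 months with the SAP's month length. For entry at 12 months (assumed), the share of the SVR12-to-3-year interval before Day 1 is (12 − 2.75)/(36 − 2.75) = 28%. At the 2-year entry limit it is (24 − 2.75)/(36 − 2.75) = 64%. That time counts as time at risk, while re-treated failures in it are filtered out. The documents give no distribution of entry times.

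**The case against.** - **The rule is pre-specified.** Protocol 8.1 and 8.1.1 contain the same exclusion and denominator, so the SAP follows the protocol's statistical section. This stands. The discrepancy lies between those sections and the endpoint wording in Protocol 5.3.2 and the synopsis.
- **A reader might infer that the SAP contradicts itself**, because SAP 6.3 counts re-treatment as failure while 5.1 removes the subject. The text does not support that: 6.3 is limited to the full analysis set, so the two rules cover different subjects. What remains is unequal handling of re-treatment before and after Day 1.
- **A reader might infer that these subjects disappear from the report.** They do not. SAP 5.1 and 8.0 list those excluded, SAP 7.3 summarises their post-treatment HCV medication, and SAP 10.2 lists re-treated subjects inside and outside the set. But the columns specified for that last listing are timing, regimens and SVR12 outcome. Loss of SVR, its date, and relapse versus reinfection are not among them. Protocol 8.1 promises a separate summary, and the SAP plans none for durability.
- **Most re-treated subjects may never have reached SVR12.** The re-treatment pathway is written mainly for failures in the prior study, and leaving those out cannot affect this endpoint. Nothing in the documents shows that any SVR12 achiever was re-treated before Day 1. This stands and limits the claim on size.
- **Restoring them may bias the other way.** Protocol 5.1 aims to recruit every virologic failure not going straight to ABT-493/ABT-530 re-treatment, with no such aim for SVR12 achievers. Criterion 3 waives the 2-year limit for re-treated subjects only, although the first note to Appendix C Table B still states that limit and needs reconciling. An all-enrolled set could therefore over-represent failures. This stands, and is why both results are needed.
- **Data are thin.** Appendix C Table B schedules no HCV RNA or resistance sample for subjects re-treated before enrolment, so some events cannot be classified. Under SAP 10.1 an event that cannot be sequenced defaults to relapse unless a genotype switch is confirmed by another assay. This stands and shapes the fix.

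**Conclusion.** The concern holds in a limited form. The analysis set removes any enrolled SVR12 achiever who lost response and was re-treated before Day 1, contrary to the endpoint as defined in Protocol 5.3.2 and the synopsis. Any bias overstates durability. This rests on one assumption: that an SVR12 achiever is re-treated only after viraemia returns.

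The number affected is not given. If it is zero, nothing changes. Otherwise the overstatement is about 0.25 to 0.5 points per subject for an assumed 400 to 200 achievers. It would go too far to say that the durability figure is known to be materially inflated, because the documents supply no count.

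Subjects barred by the exclusion criteria, such as those re-treated in Study M15-942 or given another investigational HCV drug before entry, cannot be recovered by changing the analysis set. With no hypothesis test planned and the size unknown, SHOULD-FIX is the right grade.

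**What to change.** - Reconcile Protocol 5.3.2 and the synopsis with Protocol 8.1 and 8.1.1 and SAP 5.1 and 10.2, so that one denominator is stated for each result.
- Report maintained SVR and relapse or reinfection for all enrolled SVR12 achievers exposed to ABT-493 and/or ABT-530, beside the full-analysis-set result. The exposure condition keeps the SAP's removal of subjects who received neither drug.
- Count loss of SVR before pre-enrolment re-treatment as non-maintenance. Date it at the first post-SVR12 HCV RNA at or above LLOQ (central value, otherwise local) or, if there is none, at the start of re-treatment. Exclude only HCV RNA measured after re-treatment starts.
- Show events without sequence data as *relapse or reinfection, unclassified*.
- State how many SVR12 achievers are excluded from the full analysis set, and add them to the non-maintenance listing.
- A Kaplan-Meier curve with delayed entry at Day 1 is optional. It would discard pre-enrolment events that the SAP now counts, so it cannot replace the planned curve.

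**Cost.** Revised wording, one population flag and a second column of results. Prior-study HCV RNA is already used, and re-treatment dates are collected at Day 1. For relapse in the gap between studies there may be no central RNA value, so some dates will rest on re-treatment start. The durability figure may become slightly less favourable. The all-enrolled figure needs the caveat that recruitment favours failures and that re-treated subjects have no 2-year limit under criterion 3.

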5.2 Variables Used for Stratification of Randomization

There is no randomization in this study.

6.0 Analysis Conventions

6.1 Definition of Baseline and Final Assessment

Definition of Baseline and Final Treatment Visit Value (Previous Study)

[figure not shown]
Baseline is defined as the last non-missing measurement before the first dose of study drug **in the previous study**. The final treatment visit value is defined as the last non-missing measurement collected after baseline and within 2 days of the last dose of study drug **in the previous study**.

Definition of Day 1 and Study Days (Study M13-576)

Day 1 refers to the Day 1 visit in Study M13-576. Study days in Study M13-576 are calculated for each time point relative to the Day 1 visit in this study. Study days are negative values when the time point of interest is prior to Day 1. Study days are positive values when the time point of interest is after Day 1. There is no Study Day 0. Study Days will be used to summarize hematology, clinical chemistry, and additional laboratory tests (IP-10, INR, and serum albumin) collected within this study.

Definition of Study Drug End Days (Days Relative to the Last Dose of Study Drug in the Previous Study)

Study drug end days are calculated relative to the last dose of study drug **in the previous study**. The last day of study drug is defined as Study Drug End Day 0. Days before it has negative study drug end days and days after it have positive study drug end days. Study

drug end days will be used to define the SVR windows from the previous study, and HCV RNA and resistance endpoints within this study.

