10.0 Efficacy Analyses

10.1 General Considerations

General Considerations

Plasma HCV RNA levels will be determined for each sample collected by the central laboratory using the Roche COBAS® AmpliPrep/COBAS® TaqMan® HCV Quantitative Test, v2.0. The lower limit of detection (LLOD) and lower limit of quantification (LLOQ) for this assay (regardless of genotype) are both 15 IU/mL.

HCV RNA results that are detectable but not quantifiable are reported as "< 15 IU/ML HCV RNA DETECTED" and those that are undetectable are reported as "HCV RNA NOT DETECTED" in the database.

The notation "HCV RNA < LLOQ" is used to represent all HCV RNA values < 15 IU/mL, including values reported as "HCV RNA NOT DETECTED" or "< 15 IU/ML HCV RNA DETECTED." HCV RNA ≥ LLOQ are all quantifiable values of 15 IU/mL or greater.

IL28B rs12979860 will be resulted as C/C, C/T, or T/T by the central laboratory in the previous study.

Definitions for Efficacy Endpoints

A confirmed quantifiable post-treatment value is defined as any two consecutive post-treatment HCV RNA measurements \geq LLOQ. In all relapse analyses, completion of treatment is defined as study drug duration \geq 52 days for 8-week regimens, \geq 77 days for 12-week regimens, and \geq 105 days for 16-week regimens.

ABT-493/ABT-530
M13-576 – Statistical Analysis Plan
Version 1.0 – 23 Aug 2019

 SVR_4 = HCV RNA < LLOQ in the SVR_4 window (4 weeks after the last actual dose of study drug) without any confirmed quantifiable (\geq LLOQ) post-treatment value before or during that SVR window (derived from the previous study).

 SVR_{12} = HCV RNA < LLOQ in the SVR_{12} window (12 weeks after the last actual dose of study drug) without any confirmed quantifiable (\geq LLOQ) post-treatment value before or during that SVR window (derived from the previous study).

[figure not shown]
SVR₂₄ = HCV RNA < LLOQ in the SVR₂₄ window (24 weeks after the last actual dose of study drug) without any confirmed quantifiable (\geq LLOQ) post-treatment value before or during that SVR window (derived from the previous study).

Relapse₁₂ = confirmed HCV RNA \geq LLOQ between end of treatment and 12 weeks after last actual dose of study drug (up to and including the SVR₁₂ assessment time point) for a subject with HCV RNA < LLOQ at Final Treatment Visit who completed treatment (defined above based on study drug duration in the previous study), excluding reinfection (derived from the previous study).

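### SAP 10.1 makes a suppressed end-of-treatment value a condition of reinfection, so an SVR12 achiever without one cannot be classed as reinfected, even with a proven strain switch

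*SAP*

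**What the plan says.** - **Reinfection (SAP 10.1):** confirmed HCV RNA at or above LLOQ after treatment "in a subject who had HCV RNA < LLOQ at Final Treatment Visit", together with a different genotype, subtype or clade from baseline. If phylogenetic analysis fails, a genotype assay may stand in for it. That fallback replaces only the sequencing step.
- **Final treatment value (SAP 6.1):** "the last non-missing measurement collected after baseline and within 2 days of the last dose of study drug". In SAP 6.2, Table 1, the first post-treatment window opens on Study Drug End Day 3.
- **SVR12 (SAP 10.1):** HCV RNA below LLOQ in the SVR12 "window (12 weeks after the last actual dose of study drug) without any confirmed quantifiable" value up to the end of that window. The end-of-treatment value plays no part.
- **Relapse_late (SAP 10.1):** confirmed viremia after SVR12 in a subject who achieved SVR12 "and has post-SVR₁₂ HCV RNA data available, excluding reinfection". Again there is no end-of-treatment condition.
- **Post-treatment relapse (SAP 10.1, later paragraph):** refers back to Relapse_12, Relapse_late and Relapse_overall and adds "no genotype, subtype, or clade switch compared with baseline as determined by phylogenetic analysis of the NS3 or NS5A gene sequences".
- **Maintenance of SVR (SAP 10.2):** "Overall maintenance of SVR is defined as no confirmed HCV RNA ≥ LLOQ after the" SVR12 time point. Subjects who do not maintain SVR are listed with a reason, which is either relapse or reinfection.
- **Kaplan-Meier curves (SAP 10.2):** subjects with neither event are censored at their last HCV RNA value. The second curve covers all SVR12 achievers.
- **Protocol:** an endpoint in 5.3.2 is "The percentage of subjects who relapse or have new HCV infection at any time up to the last follow-up in this study", out of SVR12 achievers who enrol. Section 8.1.1 tells relapse from new infection by the sequence of the drug target genes.

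**The concern.** Relapse and reinfection are meant to divide the late viremia seen in SVR12 achievers. Relapse points to failure of the original treatment and reinfection does not. The split works only if both definitions draw on the same subjects. Here reinfection is limited to subjects suppressed at the end of treatment, while Relapse_late is open to every SVR12 achiever with later data. A subject can have quantifiable RNA at the end of treatment, or no valid final value, and still achieve SVR12.

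For such a subject, a proven strain switch does not lead to the class that the protocol intends. The outputs at stake are the Relapse_late and reinfection counts, the reason in the non-maintenance listing, and the second Kaplan-Meier curve. The protocol has no end-of-treatment condition on this split, and SAP 12.0, which lists the departures from the protocol, does not mention one.

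**Working it through.** The plan states no figure to reproduce: it has no sample size calculation, hypothesis test or expected event count. The check is therefore one of logic, followed by the effect of a single subject.

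**Step 1. Apply the definitions.** Take an SVR12 achiever with confirmed HCV RNA at or above LLOQ after SVR12. Cross the final treatment value with presence or absence of a switch.

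| Final treatment value | Switch | Reinfection? | Relapse_late by its own sentence? | Relapse after the no-switch rule? |
|---|---|---|---|---|
| Below LLOQ, valid | Yes | Yes | No | No |
| Below LLOQ, valid | No | No | Yes | Yes |
| Quantifiable or missing | Yes | **No** | **Yes** | **No** |
| Quantifiable or missing | No | No | Yes | Yes |

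Rows 1, 2 and 4 each give one consistent class. Row 3 does not. Reinfection fails on the end-of-treatment condition. The Relapse_late sentence captures the event because it excludes only events that meet the reinfection definition. The later paragraph rejects relapse because of the switch. The answer depends on which sentence governs, and neither answer is reinfection.

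**Step 2. Follow row 3 through the outputs.**

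- Maintenance of SVR: counted as not maintained, because that definition does not use the final treatment value.
- Non-maintenance listing: if the no-switch rule governs, neither permitted reason applies.
- Second Kaplan-Meier curve: if the no-switch rule governs, the subject is censored although counted as a failure in the maintenance table. If the Relapse_late sentence governs, the subject is a relapse event despite the switch.
- First Kaplan-Meier curve: not affected, because it is restricted by design: "For the first Kaplan-Meier curve among subjects with final on-treatment HCV RNA < LLOQ".

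**Step 3. A route by which this can occur.** SAP 10.1 counts at least 52, 77 and 105 days as completion of 8-, 12- and 16-week regimens. The shortfalls are 56 − 52 = 4, 84 − 77 = 7 and 112 − 105 = 7 days. A completer who stops that early but is sampled on the planned last day has that sample at Study Drug End Day 4 to 7, beyond Day 2. An earlier on-treatment sample then supplies the final value, and it may be quantifiable. This shows that the case is possible, not that it is common.

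**Step 4. Effect of one subject.** The number of SVR12 achievers in the full analysis set is not given. About 400 subjects are planned in total, so 200 to 400 is assumed. The change in the Relapse_late percentage is 100 / N; the limits are exact (Clopper-Pearson) 95% limits.

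| Assumed N | Change per subject | 0 late relapses | 1 late relapse |
|---|---|---|---|
| 400 | 0.25 points | 0% (0 to 0.92) | 0.25% (0.01 to 1.38) |
| 300 | 0.33 points | 0% (0 to 1.22) | 0.33% (0.01 to 1.84) |
| 200 | 0.50 points | 0% (0 to 1.83) | 0.50% (0.01 to 2.75) |

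The reinfection count is one too low on either reading. Relapse_late is one too high only if its own sentence governs.

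**The case against.** The best defence is that this is a narrow drafting gap. It needs two things in one subject: a quantifiable or missing final treatment value followed by SVR12, and a later switch. The documents give no frequency for either. The main durability result does not change, every non-maintainer is listed individually so an odd case would be seen, and the analysis is descriptive. SAP 12.0 also says that relapse and maintenance of SVR matter more than the reinfection rate. All of this stands and limits the weight of the point. It does not make the definitions consistent, and the stated interest in relapse is a reason to keep reinfections out of that count.

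A reader might infer more, in three ways that the documents do not support:

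- **That any last sample taken more than 2 days before the last dose is invalid.** This reads the SAP 6.1 limit as a band on both sides of the last dose. Asking for the last value after baseline, opening the post-treatment windows on Day 3, and calling the value the final on-treatment one in SAP 10.2 all favour an upper cut-off at Study Drug End Day 2. On that reading an earlier sample below LLOQ still counts. The wording is loose, but an error is not shown.
- **That such events necessarily become late relapses and inflate the failure count.** If the no-switch rule governs, as it does when the two paragraphs are read together, the result is neither class.
- **That subjects are wrongly lost from the first Kaplan-Meier curve.** Protocol 8.1.1 itself limits that curve to subjects below LLOQ at the end of treatment.

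**Conclusion.** The reinfection definition in SAP 10.1 is wrong as written, on a small scale. An SVR12 achiever with a quantifiable or missing final treatment value and a later confirmed strain switch cannot be classed as reinfected. Two sentences of the same section then disagree on whether the event is a late relapse. This holds under either reading of the 2-day limit, and it departs from the sequence-based rule in Protocol 8.1.1 without being listed as a change.

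Overall maintenance of SVR is unaffected. Each case leaves reinfection one short and, on one of the two readings, adds one late relapse: 0.25 percentage points at 400 SVR12 achievers and 0.50 at 200, both assumed denominators. How many cases to expect cannot be derived from the documents; it is likely few or none. The correction is still worth making: if late relapses are few, the counts themselves are the result, and one against none would be noticed.

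**What to change.** In SAP 10.1, define reinfection as confirmed post-treatment HCV RNA at or above LLOQ, with a genotype, subtype or clade switch from baseline, in a subject who either had HCV RNA below LLOQ at the Final Treatment Visit or achieved SVR12. Row 3 of the first table then becomes reinfection and the other rows stay as they are, so every confirmed late viremia in an SVR12 achiever falls in exactly one class.

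As a clarification only, state in SAP 6.1 that the final treatment value is the last non-missing one after baseline and on or before Study Drug End Day 2.

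The cost is one clause and one clarified sentence. No new data are needed, and the maintenance analysis and the population of the first Kaplan-Meier curve stay as intended. If the end-of-treatment condition is kept on purpose, SAP 12.0 should list it as a departure from the protocol, and SAP 10.1 should say which class the row 3 subject belongs to.
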